- **Screening and baseline period:** Screening should occur during the last visit of the originating study unless the patient received oral systemic AD treatment as rescue therapy during the originating study and needs additional time to complete the required 4-week washout period or the sponsor gave approval.
- **Treatment Period 1:** Treatment period from Week 0 to Week 52. Patients will be classified as responders, partial responders or nonresponders at the entry of Study JAHN based on the criteria given in Section 5.1.

- Treatment Period 2: Treatment period from Week 52 to 200 and will contain a randomized withdrawal and downtitration substudy. At Week 52, all patients will be evaluated for substudy eligibility, and the criteria are given in the Protocol. Patients not entered in the substudy will continue on their current treatment.
- Posttreatment follow-up period: Period from Week 200 (Visit 22) or Early Termination Visit (ETV) to approximately 28 days after the last dose of IP.

Abbreviations: BARI = baricitinib; IGA = Investigator’s Global Assessment; TCS = topical corticosteroids.

a Background TCS may be initiated or reinitiated at any time during the study, following the guidelines in the Protocol (Section 7.7.1) and will be provided as part of rescue or retreatment any time a patient’s IGA score becomes ≥ 3 as described in the Protocol (Sections 5.1.2.1 and 5.1.3.1).

b Eligible patients will be rerandomized in the withdrawal and downtitration substudy as described in the Protocol (Section 5.1.3.1). Patients who do not enroll in the substudy will remain on their treatment.

c Patients enrolled in the substudy will automatically be retreated if their IGA score becomes ≥ 3 as described in the Protocol (Section 5.1.3.1).

d Rescue is available as described in the Protocol (Section 5.1.2.1).

Figure JAHN.5.1. Illustration of study design for Clinical Protocol I4V-MC-JAHN.

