BARI 2 mg	BARI 2 mg followed to end of Treatment Period 1 or censored at dose or treatment change
PBO/BARI 1 mg/BARI 2 mg to BARI 4 mg	PBO/BARI 1 mg/BARI 2 mg switching to BARI 4 mg at entry to Study JAHN followed to end of Treatment Period 1 or censored at dose or treatment change
BARI 4 mg	BARI 4 mg followed to end of Treatment Period 1 or censored at dose or treatment change
Pooled BARI	BARI 1 mg/BARI 2 mg/BARI 4 mg at entry to Study JAHN followed to end of Treatment Period 1 or censored at dose or treatment change
Treatment Groups for Treatment Period 2 (Week 52-200)	Definition
BARI 2 mg to PBO	Randomized to PBO in Treatment Period 2 (previously treated with BARI 2 mg) followed to end of study or censored at retreatment with BARI 2 mg

Treatment Groups for Treatment Period 2 (Week 52-200)	Definition
BARI 2 mg to BARI 1 mg	Randomized to BARI 1 mg in Treatment Period 2 (previously treated with BARI 2 mg) followed to end of study or censored at retreatment with BARI 2 mg
BARI 2 mg to BARI 2 mg	Randomized to stay on BARI 2 mg in Treatment Period 2 followed to end of study
BARI 4 mg to PBO	Randomized to PBO in Treatment Period 2 (previously treated with BARI 4 mg) followed to end of study or censored at retreatment with BARI 4 mg
BARI 4 mg to BARI 2 mg	Randomized to BARI 2 mg in Treatment Period 2 (previously treated with BARI 4 mg) followed to end of study or censored at retreatment with BARI 4 mg
BARI 4 mg to BARI 4 mg	Randomized to stay on BARI 4 mg in Treatment Period 2 followed to end of study
BARI 2 mg	Not part of the substudy, stayed on BARI 2 mg in Treatment Period 2 followed to end of study (this treatment group includes the open-label BARI 2 mg addendum patients)
BARI 4 mg	Not part of substudy, stayed on BARI 4 mg in Treatment Period 2 followed to end of study
Treatment Group for Treatment Periods 1 and 2 (Week 0-104) (for Box Plots Only)	Definition
PBO	Placebo at entry to Study JAHN followed to end of study or censored at treatment change
BARI 1 mg	BARI 1 mg followed to end of study or censored at dose or treatment change
BARI 2 mg to PBO	BARI 2 mg in Treatment Period 1, rerandomized to PBO in Treatment Period 2 followed to end of study or censored at retreatment with BARI 2 mg
BARI 2 mg to BARI 1 mg	BARI 2-mg in Treatment Period 1, rerandomized to BARI 1 mg in Treatment Period 2 followed to end of study or censored at retreatment with BARI 2 mg

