BARI 2 mg to BARI 2 mg	BARI 2 mg in Treatment Period 1, rerandomized to stay on BARI 2 mg in Treatment Period 2 followed to end of study
BARI 4 mg to PBO	BARI 4 mg in Treatment Period 1, rerandomized to PBO in Treatment Period 2 followed to end of study or censored at retreatment with BARI 4 mg
BARI 4 mg to BARI 2 mg	BARI 4 mg in Treatment Period 1, rerandomized to BARI 2 mg in Treatment Period 2 followed to end of study or censored at retreatment with BARI 4 mg
BARI 4 mg to BARI 4 mg	BARI 4 mg in Treatment Period 1, rerandomized to stay on BARI 4 mg in Treatment Period 2 followed to end of study
BARI 2 mg	BARI 2 mg in Treatment Period 1, did not enter the substudy and stayed on BARI 2 mg in Treatment Period 2 followed to end of study (this treatment group includes the open label BARI 2 mg addendum patients)
BARI 4 mg	BARI 4 mg in Treatment Period 1, did not enter the substudy and stayed on BARI 4mg in Treatment Period 2 followed to end of study

Abbreviations: BARI = baricitinib; PBO = placebo.

An all-baricitinib exposure, defined as patients valid for the safety population with at least 1 dose of baricitinib anytime during Study JAHN, will be analyzed for the final analysis (final datalock).

Follow-up population: The follow-up population is defined as patients who entered the follow-up period and completed the follow-up visit.

For the February 2021 DBL, adverse event (AE) Period 1 tables will be summarized by treatment in Period 1, which include treatment group of (PBO, BARI 1-mg, BARI-2mg, BARI 4-mg, Pooled BARI).

For final DBL, AE tables will be summarized by treatment in Period 2 as specified in [Table JAHN.6.1](#).

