6.14. Safety Analyses

Detailed analyses and discussion of Study JAHN safety data are more thoroughly assessed in the context of combining the safety data from the originating Studies, JAHL, JAHM, and JAIY with the safety data from Study JAHN. The planned analyses are described in the compound level safety standards.

For the purpose of Study JAHN alone, the following are planned to be analyzed:

- duration of exposure by Treatment Periods 1 and 2
- overview of AEs by Treatment Periods 1 and 2
- treatment-emergent adverse events (TEAEs) by PT nested within System Organ Class (SOC) by Treatment Periods 1 and 2
- serious adverse events (SAEs) by PT nested within SOC by Treatment Periods 1 and 2, and listing of SAEs in Treatment Periods 1 and 2 combined (one listing)
- AEs leading to permanent study drug discontinuation by PT nested within SOC for Treatment Period 1, and listing of AEs leading to permanent study drug discontinuation and discontinuation from the study in Treatment Periods 1 and 2 combined (one listing)
- listing of deaths in Treatment Periods 1 and 2 combined (1 listing), if any
- clinical laboratory evaluation and vital signs in terms of box plots, descriptive and treatment-emergent summaries in Treatment Period 1
- clinical laboratory and vital signs in terms of box plots and descriptive summaries in Treatment Periods 1 and 2 combined

The general methods used to summarize safety data, including the definition of baseline value, are described in Section 6.2.

Safety analyses will be conducted according to the safety population defined in Section 6.2.1 and the treatment groups defined in Table JAHN.6.1 in Section 6.2.1.

Unless otherwise specified, by-visit summaries will include planned on-treatment visits. For tables that summarize events (such as AEs), on-treatment and follow-up data will be included up to 30 days after the last dose of treatment or up to dose or treatment change, where applicable.

For the February 2021 DBL and Final DBL summary and analyses, safety analyses will be done for the disposition summary and the below AE tables summarized in Period 1 and Period 2, respectively. Other detailed safety assessments will be implemented in the integrated safety analysis plan with other studies (I4V-MC-JAIN, I4V-MC-JAIW, and I4V-MC-JAIX).

- overview of AEs
- TEAEs
- AEs leading to permanent discontinuation of study drug
- SAEs

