6.14.2. Adverse Events

Adverse events are recorded in the eCRFs. Each AE will be coded to SOC and PT using the MedDRA version that is current at the time of DBL. Severity of AEs is recorded as mild, moderate, or severe. TEAEs will be analyzed by Treatment Periods 1 and 2.

A TEAE is defined as an event that first occurred or worsened in severity after the first dose of study treatment in Study JAHN and on or prior to the last visit date during the analysis period. The analysis period is defined as the treatment period plus up to 30 days off-drug follow-up time.

Adverse events are classified based upon the MedDRA PT. The MedDRA Lowest Level Term (LLT) will be used in defining which events are treatment emergent. The maximum severity for each LLT during the baseline period up to first dose of the study medication in Study JAHN will be used as baseline. If an event with missing severity is preexisting during the baseline period, and persists during the treatment period, then the baseline severity will be considered mild for determining treatment emergence (ie, the event is treatment emergent if the severity is coded moderate or severe postbaseline and not treatment emergent if the severity is coded mild postbaseline). If an event occurring postbaseline has a missing severity rating, then the event is considered treatment emergent unless the baseline rating is severe, in which case the event is not treatment emergent. The day and time for events where onset is on the day of the first dose of study treatment will both be used to distinguish between pretreatment and posttreatment in order to derive treatment-emergence. Should there be insufficient data for AE start date to make this comparison (eg, the AE start year is the same as the treatment start year, but the AE start month and day are missing), the AE will be considered treatment emergent.

In general, summaries will include the number of patients in the safety population (N), frequency of patients experiencing the event (n), and relative frequency (ie, percentage; $n/N*100$). For any events that are gender specific based on the displayed PT, the denominator used to compute the percentage will only include patients from the given gender.

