In an overview table, the number and percentage of patients in the safety population who experienced death, an SAE, any TEAE, discontinuation from the study due to an AE, permanent discontinuation from study drug due to an AE, or a severe TEAE will be summarized by treatment group.

The number and percentage of patients with TEAEs will be summarized by treatment group for both Treatment Periods 1 and 2 by MedDRA PT nested within SOC with decreasing frequency in SOC, and events ordered within each SOC by decreasing frequency in the baricitinib 4-mg group.

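### Period 2 adverse-event percentages are shown side by side for randomized arms whose follow-up ends by different rules, and no time-at-risk rate is planned

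*SAP*

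**What the plan says.** **Measure.** SAP 6.14.2 says that AE summaries will in general give N, "frequency of patients experiencing the event (n), and relative frequency", computed as n/N*100. It applies this to Period 2: "The number and percentage of patients with TEAEs will be summarized by treatment group for both Treatment Periods 1 and 2". Section 6.14.2.2 does the same for serious AEs.

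**Tables at the final lock.** Section 6.2.1: "For final DBL, AE tables will be summarized by treatment in Period 2 as specified in" Table JAHN.6.1. Section 6.14 lists the tables: AE overview, treatment-emergent AEs, AEs leading to permanent discontinuation of study drug, and serious AEs.

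**Follow-up by arm (Table JAHN.6.1, Period 2, headed Weeks 52 to 200).**
- Moved from 2 mg to placebo or to 1 mg: "followed to end of study or censored at retreatment with BARI 2 mg". The two arms moved down from 4 mg have the same rule, with retreatment at 4 mg.
- Kept on 2 mg: "Randomized to stay on BARI 2 mg in Treatment Period 2 followed to end of study". The arm kept on 4 mg has the same rule. Neither has a cut-off at retreatment.

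**What ends follow-up.** The notes to the design figure in SAP 5.1 state: "Patients enrolled in the substudy will automatically be retreated if their IGA score becomes" 3 or more. Section 6.14 counts events up to 30 days after the last dose "or up to dose or treatment change, where applicable".

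**Exposure.** Section 6.14.1 totals patient-years per group and period. No section of the SAP divides AE counts by time at risk.

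**A second censoring rule.** SAP 6.4 defines a Period 2 rule that censors at permanent discontinuation or retreatment. It applies the rule to both efficacy and safety in the substudy and exempts no arm.

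**The concern.** The substudy re-randomizes patients 1:1:1 within each entry dose (SAP 5.2), so a reader of the Period 2 AE tables will set the columns against one another. The columns do not cover the same length of observation. In four of the six arms, observation stops when disease control is lost, which is what withdrawal or down-titration may provoke. In the other two, Table JAHN.6.1 lets it run on. A patient seen for longer has more chance of at least one event, so n/N rises with follow-up even when the hazard is the same.

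Continued baricitinib could therefore appear to carry several times the AE burden of placebo when the true rates are equal, and a real excess on the withdrawn arm could be hidden or reversed. Table JAHN.6.1 also makes follow-up depend on outcome, so the distortion is not random noise.

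**Working it through.** The documents give no AE rate, retreatment rate or power figure for this point, so there is no planned figure to reproduce. The following is an illustration, and every rate in it is an assumption.

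**Inputs from the plan.** Period 2 lasts at most 200 − 52 = 148 weeks, so T = 148 × 7 / 365.25 = 2.836 years. Retreatment censors the withdrawn and down-titrated arms. The continued arms have no such censoring under Table JAHN.6.1.

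**Assumptions.** Constant first-event hazard λ, equal in both arms. Constant dropout hazard d, equal in both arms. Exponential retreatment with hazard μ, set by the proportion p retreated by 16 weeks: μ = −ln(1 − p) / (16 × 7 / 365.25). This gives μ = 2.260, 1.163 and 0.728 per year for p = 50%, 30% and 20%.

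**Formulas.** With h = λ + μ + d (μ = 0 where retreatment does not censor):
- crude proportion n/N = (λ/h) × (1 − exp(−hT))
- mean time at risk to first event or censoring = (1 − exp(−hT)) / h
- first-event rate = the first divided by the second, which is λ in either arm.

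**Worked case: λ = 0.2, p = 50%, d = 0.15.**
- Withdrawn: h = 2.610; n/N = (0.2 / 2.610) × (1 − exp(−7.40)) = 7.7%.
- Continued: h = 0.35; n/N = (0.2 / 0.35) × (1 − exp(−0.993)) = 36.0%.
- The rate is 20 per 100 patient-years in both.

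**Range at λ = 0.2.** Mean follow-up ignores events.

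| Withdrawn arm retreated by 16 weeks | Continued arm censored at retreatment by 16 weeks | Dropout per year | Mean follow-up, weeks | Crude n/N, withdrawn v continued |
|---|---|---|---|---|
| 50% | none | 0.15 | 22 v 121 | 7.7% v 36.0% |
| 30% | none | 0.15 | 39 v 121 | 13.0% v 36.0% |
| 20% | none | 0.5 | 41 v 79 | 13.8% v 24.6% |
| 50% | 20% (6.4 reading) | 0.15 | 22 v 55 | 7.7% v 17.7% |
| 50% | 50% (6.4 reading) | 0.15 | 22 v 22 | 7.7% v 7.7% |

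The first-event rate is 20 per 100 patient-years in both arms in every row.

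**Other hazards** (50% retreated, dropout 0.15, no censoring of the continued arm): 2.0% v 10.8% at 5 per 100 patient-years, and 17.2% v 64.8% at 50.

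**Reversal.** Give the withdrawn arm twice the hazard (40 v 20 per 100 patient-years; 50% retreated, dropout 0.15). Then h = 0.4 + 2.260 + 0.15 = 2.810 and n/N = (0.4 / 2.810) × (1 − exp(−7.97)) = 14.2%, against 36.0%. The percentages point the wrong way.

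**The case against.** **No clear Period 2 comparison is planned.** This stands. The final-lock AE tables are described as summaries by group. A reader might infer a formal test of baricitinib against placebo on these percentages, because SAP 6.2.3 specifies Fisher's exact test for AE proportions. That sentence sits in a paragraph that opens with the US submission lock, and nothing clearly carries it to Period 2 at the final lock. The point is about display and interpretation.

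**The follow-up contrast is easily exaggerated.** This also stands. A reader might set 16 weeks against 148 weeks, which at 20 per 100 patient-years gives 1 − exp(−0.2 × 0.307) = 5.9% v 1 − exp(−0.2 × 2.836) = 43.3%. The documents do not support that as typical. They give no time to retreatment, patients who keep their response stay in follow-up, and the phased roll-off described in the SAP revision history ends some patients' participation before Week 200. The scenarios in the table are milder for that reason.

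**SAP 6.4 may remove much of the asymmetry.** Partly right. If its rule governs safety, the continued arms are censored at retreatment as well. The gap then depends on how far retreatment differs between arms: 7.7% v 17.7% in one row, none if retreatment is equal. But 6.4 and Table JAHN.6.1 cannot both apply to the continued arms, so the imbalance cannot be taken as settled in either direction.

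**Exposure is reported and detail is deferred.** Group patient-years would let a reader see the imbalance, but total exposure is not time to first event. Exposure-adjusted rates may exist in the compound-level standards or the integrated plan, which are not part of these documents. Section 6.14 sends other assessments there; the four AE tables belong to this study.

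**The wording of 6.14.2 is not exclusive.** True: the listed statistics are what summaries will include in general. Still, no section adds a rate.

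**Conclusion.** The point holds as a defect in presentation and interpretation. As written, the final-lock Period 2 AE tables put percentages side by side for randomized arms whose observation ends by different rules, partly driven by relapse, with no measure that allows for it. At an assumed equal hazard of 20 per 100 patient-years, the withdrawn arm reads 7.7% to 13.8% and the continued arm 24.6% to 36.0% under Table JAHN.6.1. These figures rest on constant hazards, exponential retreatment and dropout, and rates chosen for illustration. The direction follows from the censoring rules; the size does not come from the documents.

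Confidence in the size is moderate at best, because the SAP gives two rules for the continued arms. A reader should not infer a planned invalid significance test, or that every continued-dose patient is observed to Week 200. Neither is in the text.

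This should be changed, though it does not undermine the study. A rate per patient-year is itself only approximate, since censoring at relapse is informative.

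**What to change.** 1. Reconcile SAP 6.4 with Table JAHN.6.1: state whether the continued-dose arms are censored at retreatment for safety, and use one rule throughout.
2. In the Period 2 overview, treatment-emergent AE, serious AE and discontinuation-AE tables, add patients with a first event per 100 patient-years at risk, with a 95% CI, beside n and the percentage. Derive time at risk for each row, to first event or censoring, over the same window used to count the events. The exposure in 6.14.1 cannot be reused as it stands: it is total exposure, and it stops at the last dose while AEs are counted for up to 30 days afterwards.
3. Correct the Period 2 exposure formula in 6.14.1. Its upper bound is given only as a date later than Week 52; it needs an actual end date.
4. Footnote these tables to say that crude percentages are not comparable across the Period 2 groups and that censoring at relapse is informative.
5. Add a companion summary over a common early window, Weeks 52 to 68. This limits the difference in observation time but does not remove it, because early retreatment still censors.

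Cost: modest extra programming, mainly the time-at-risk derivation for each row, and wider tables. No new data collection.

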6.14.2.1. Common Adverse Events

Common TEAEs will not be analyzed for Study JAHN data alone.

6.14.2.2. Serious Adverse Event Analyses

Consistent with the International Conference on Harmonisation (ICH) E2A guideline (ICH 1994) and 21 Code of Federal Regulations (CFR) 312.32 (a) (CFR 2010), an SAE is any AE that results in any one of the following outcomes:

- death
- initial or prolonged inpatient hospitalization
- a life-threatening experience (ie, immediate risk of dying)
- persistent or significant disability/incapacity
- congenital anomaly/birth defect

Important medical events that may not be immediately life-threatening or result in death or hospitalization but may jeopardize the patient or may require intervention to prevent one of the other outcomes listed in the definition above. See examples in the ICH E2A guideline Section 3B.

The number and percentage of patients who experienced any SAE will be summarized by treatment group for each Treatment Periods 1 and 2 using MedDRA PT nested within SOC. Events will be ordered by decreasing frequency in the baricitinib 4-mg group within decreasing frequency in SOC.

An individual listing of all SAEs will be provided. A listing of deaths, regardless of when they occurred during the study, will also be provided.

6.14.2.3. Other Significant Adverse Events

Other significant AEs to be summarized will provide the number and percentage of patients who permanently discontinued study drug because of an AE or death by treatment group for Treatment Period 1 using MedDRA PT nested within SOC. Events will be ordered by decreasing frequency in the baricitinib 4-mg group within decreasing frequency in SOC.

A listing of all AEs leading to permanent discontinuation from the study drug or from the study will be provided for both Treatment Periods 1 and 2.

6.14.2.4. Criteria for Notable Patients

Patient narratives will be provided for all patients who experience certain “notable” events prior to data cutoff for the submission. See compound level safety standards for list of criteria.

6.14.3. Clinical Laboratory Evaluation

For the categorical laboratory analyses (shift and treatment emergent), the analysis period is defined as the treatment period plus up to 30 days off-drug follow-up time. The analysis period for the continuous laboratory analyses (eg, change from baseline by time point) is defined as the treatment period excluding off-drug follow-up time.

All laboratory tests will be presented using the International System (SI) and US conventional (CN) units. The performing central laboratory reference ranges will be used to define the low and high limits.

There is one special circumstance for laboratory values to be derived based on regularly scheduled, protocol-specified analytes. The low-density lipoprotein/high-density lipoprotein (LDL/HDL) ratio will be derived as the ratio of LDL cholesterol to HDL cholesterol. There are no central lab reference ranges for the LDL/HDL ratio.

The following will be conducted for the laboratory analytes collected quantitatively:

- **Box plots:** Values at each visit (starting at first visit in Study JAHN) and change from last baseline to each visit and to last postbaseline measure will be displayed in box plots for patients who have both a baseline and at least 1 postbaseline visit. The last nonmissing observation in the treatment period will be used as the last observation. Box plots will be provided for Treatment Period 1 and for Treatment Periods 1 and 2 combined. Individual measurements outside of reference limits will also be displayed using distinct symbols overlaying the box plot. Original-scale data will be used for the display but for some analytes (eg, immunoglobulins) a logarithmic scale may be used to aid in viewing the measures of central tendency and dispersion. Unplanned measurements will be excluded. Descriptive summary statistics will be included below the box plot along with p-values resulting from between-treatment comparison in change from last baseline to last observation. An ANCOVA model with explanatory term for treatment and the baseline value as a covariate will be used. These box plots will be used to evaluate trends over time and to assess a potential impact of outliers on central tendency summaries.
- **Treatment-emergent high/low analyses:** The number and percentage of patients with treatment-emergent high and low laboratory results at any time during Treatment Period 1 will be summarized by treatment group. Planned and unplanned measurements will be included. A treatment-emergent **high** result is defined as a change from a value less than or equal to the high limit at all baseline visits to a value greater than the high limit at any time during the treatment period. A treatment-emergent **low** result is defined as a change from a value greater than or equal to the low limit at all baseline visits to a value less than the low limit at any time during the treatment period. The Fisher's exact test will be used for the treatment comparison.

For laboratory analyte measurements collected qualitatively, a listing of abnormal findings will be provided for both treatment periods combined. The listing will include but will not be limited to patient ID, treatment group, laboratory collection date, analyte name, and analyte finding.

